### 3.4 CRITERIA FOR ADDITIONAL TREATMENT

Patients will be eligible to continue to receive mithramycin for as long as they do not experience clinical or radiographic disease progression (See section 6.4) and tolerate mithramycin (as defined in Section 3.3).

Patients may receive the next course of mithramycin at the same dose level (or reduced level as above) provided the following criteria are met by day 21.

- patient has stable or responding disease;
- has a platelet count  $\geq 75,000/\mu\text{L}$  (transfusion independent), and an ANC  $\geq 1000/\mu\text{L}$ , and meets other laboratory parameters defined in the eligibility section; and
- has not met any criteria for removal from treatment or off study (Section 3.6)

### **3.5 ON STUDY PROTOCOL EVALUATION (APPENDIX 2: STUDY CALENDAR)**

#### **3.5.1 Baseline Evaluations**

- Total and fractionated serum bile acid levels within 2 weeks prior to treatment. *Note: results need not be back prior to commencing treatment.*
- Liver elastography assessment by ultrasound within 2 weeks prior to treatment

#### **3.5.2 Monitoring During Treatment:**

- Physical exam, to include vital signs, weight, toxicity evaluation and ECOG status within 4 days of each treatment cycle.
- Toxicity assessment during cycles 1 and 2: daily during treatment and then weekly. During cycle 3 and subsequent cycles, twice weekly during treatment and then weekly.
- Laboratory evaluations:
  - CBC with differential count within 2 days prior to treatment and daily during drug administration (days 1-7 prior to each infusion, active treatment week); then twice weekly on off-treatment weeks of cycles 1-2. During subsequent cycles: CBC with differential count within 2 days prior to commencing treatment and twice weekly during administration prior to infusion, then weekly.
  - Chemistry: sodium, potassium, chloride, CO2, creatinine, glucose, BUN, albumin, ionized calcium\*, magnesium, alkaline phosphatase, ALT/GPT, AST/GOT, total bilirubin, total protein daily within 2 days of commencing treatment and during drug administration (days 1-7 prior to each infusion, active treatment week); then twice weekly on off-treatment weeks of cycles 1-2. During subsequent cycles chemistries are performed weekly.
  - Coagulation Studies: PT/PTT/Thrombin Time, Fibrinogen prior to day 1 and on days +4 and +8 of every cycle.
  - Total and fractionated bile acids within 2 days prior to and on day +7 of every treatment cycle and at time of treatment evaluation at the end of the 3rd cycle of therapy.

**Note:** The patient may have evaluations and lab work obtained through his or her local physician between cycles and have the results faxed to the Research Nurse. The Research RN will contact the patient as noted above to discuss toxicity.

\* Ionized calcium is not part of a standard lab panel and could be omitted if not available or not covered by insurance when performed outside NIH.

- 12-Lead EKG:
  - Cycles 1 and 2: Days 1, 4, and 7, before infusion within 1 hour of pre infusion PK sample to evaluate for QT prolongation potential

**Note:** although it is preferable to have the EKGs done within 1 hour of PK sample collection, EKGs may be done outside of the specified times if unexpected events in clinic or floor prevent staff from conducting the study within the specified timeframe. EKGs performed outside of this window will NOT be considered protocol deviations.

- Cycle 3 and subsequent cycles: Within 1 hour of start of infusion on day 1 and day 7.
- Tumor Measurements: CT scan of the chest, abdomen and pelvis, brain MR scan as clinically indicated, as well as FDG-PET and other standard-of-practice scans relevant to each patient's malignancy, as well as liver elastography by ultrasound will be performed two weeks (plus 12 or minus 3 days) after every course of therapy (three cycles).

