#### **1.3.4 Recent Experience with Mithramycin in Adult Oncology Patients at the NCI**

Twelve patients (10 males; 2 females; median age 51y; range 40-72y) with refractory thoracic malignancies (six MPMs, 2 esophageal cancers, two lung cancers, 2 synovial sarcomas) received 6h mithramycin infusions q day x 7, every 28 days. Response rates following two cycles, pharmacokinetics, and systemic toxicities (cycle 1) were evaluated. A total of 20 cycles were administered to 12 patients; all were evaluable for toxicities. No objective responses were observed in 7 patients who were evaluable for treatment responses. No myelosuppression, uncontrollable nausea or vomiting was observed. No patients experienced bleeding. The lack of these toxicities, which have been associated with mithramycin treatment  may be attributable at least in part to higher purity of the current drug relative to what had been used previously.

Eight patients experienced transient, asymptomatic dose-limiting transaminitis following 25mcg/kg/infusions. This toxicity always occurred on day 4 of the infusion. Percutaneous biopsies from three individuals revealed apoptotic hepatocellular death (**Figure 6A**). Four patients (two with MPM) had no hepatotoxicity and tolerated dose escalation to 30 mcg/kg/infusion. Peak and steady state mithramycin levels were 20 and 8nM, respectively, which were not different in patients with or without hepatotoxicity (**Figure 6B**). DMET genotyping revealed that two SNPs (rs2302387 and rs4668115) in genes encoding two related bile transporters (ABCB4 and ABCB11, respectively) were significantly associated with LFT elevations in the 12 patients treated with mithramycin (**Figure 7A** and **Figure 7B**).

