### 3.3 DOSING DELAYS AND MODIFICATIONS

#### General guidelines for treatment modifications:

Adverse Events: All adverse events in this trial will be graded using the NCI Common Terminology Criteria for Adverse Events (CTCAE) version 4.0 - a complete listing is available at the CTEP website: <http://ctep.cancer.gov/forms/CTCAEv4.pdf>.

Dose adjustments will be made according to the guidelines below, with dose levels defined as follows:

Dose Level	Mithramycin Dose
2	50 mcg/kg
1	30 mcg/kg
-1	25 mcg/kg
-2	18 mcg/kg

Summary of dose holding/interruptions and dose de-escalation recommendations for mithramycin in case of mithramycin -related adverse events (graded according to NCI-CTCAEv4.0)

General Adverse Events	Action
Non-hematological, Grade 1 or 2 (excluding hemorrhage)	
 
Continue mithramycin therapy at full dose prescribed.
 
Apply maximum supportive care recommendations.
 
If prolonged duration of Grade 2 adverse event (<math>\geq 7</math> days) is affecting quality of life, start the next treatment cycle at DL -1.
 
If event persists and continues to affect quality of life for <math>\geq 7</math> more days following initial dose reduction, start the next treatment cycle at DL -2.
 
If events continue to persist, discontinue drug.
 

Grade 3 ALT and AST	
 
Hold mithramycin therapy until recovery to Grade <math>\leq 1</math> (up to 21 days of start of cycle).
 
If ALT and AST resolve to Grade <math>\leq 1</math> within 21 days, maintain current dose level.
 
If ALT and AST do NOT resolve to Grade <math>\leq 1</math> within 21 days, dose reduce 1 level.
 
If grade 4 ALT or AST occur in a subsequent cycle, dose reduce 1 level independent of the date of resolution.
 

Grade 4 ALT and AST	
 
Hold mithramycin therapy until recovery to Grade <math>\leq 1</math> (up to 21 days of start of cycle).
 
If ALT and AST resolve to Grade <math>\leq 1</math> within 21 days,
 

General Adverse Events	Action
	
reduce 1 level.
 
 
• If grade 4 ALT or AST occur in a subsequent cycle, dose reduce 1 level independent of the date of resolution.
 

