13.3.2 Appendix 2: Study Calendar

		Cycles 1 and 2							
Research Eligibility Evaluation/Baseline		Week 1							Week 2
		day 1	day 2	day 3	day 4	day 5	day 6	day 7	
Mithramycin		x	x	x	x	x	x	x	
Histologic path confirmation	x								
ABCB4 and ABCB11 status	X								
Informed consent	x								
Medical history	x								
Concurrent meds	x								
Physical examination	x	x i							
Performance status	x	x i							
General labs	x	x	x	x	x	x	x	x	xx b
Serum bile acids (total and fractionated)	x	x						x	
Coagulation labs	x				x				x c
Pregnancy test	x								
Cardiac function tests	x								
Imaging studies incl liver Elastograpy by ultrasound	x								
Adverse events		←—————→							
Tumor biopsy	x								
Research labs		x d							x c
PK	x	x df	x df		x df			x df	x g
EKG	X	x d			x d			x d	

		Cycles 3 and beyond*						
		Week 1					Week 2	
		day 1	day 2	day 3	day 4	day 5	day 6	day 7
Mithramycin		x	x	x	x	x	x	x
Histologic path confirmation								
Informed consent								
Medical history								
Concurrent meds								
Physical examination		x i						

**Abbreviated Title:** Mithramycin for Cancer Stem Cells

**Version Date:** 09/14/2018

	Cycles 3 and beyond*							
	Week 1							Week 2
	day 1	day 2	day 3	day 4	day 5	day 6	day 7	
Performance status	x i							
General labs				x h			x	x a
Coagulation labs				x				x c
Serum bile acids (total and fractionated)	x						x	x e (course 1 only)
Pregnancy test								
Cardiac function tests								
Imaging studies including liver elastography by ultrasound								x e
Adverse events								
Tumor biopsy								
Research labs	x d							x c
EKG	x d						x d	
a - once weekly								
b - twice weekly								
c - day 8 of cycle (same as day 1 of week 2)								
d -prior to dosing								
e – two weeks (plus 12 or minus 3 days ) after the end of each course (1 course = 3 cycles)								
f - end of infusion								
g - 24 and 48 hours after day 7 infusion								
h- CBC with differential only								
i – within 4 days prior to the start of each cycle								
*Patients will continue to receive treatment until criteria for removal from protocol or off-study criteria are met (See section 3.6)								

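### From cycle 3 no ALT/AST is scheduled on day 4, the day on which dose-limiting transaminitis was reported, so the plan's own hold rule can act three doses late

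*Combined protocol and SAP*

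**What the plan says.** **Cycles 1 and 2.** Section 3.5.2 has chemistries, ALT and AST included, before each infusion on days 1 to 7 and twice weekly afterwards.

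**Cycle 3 onward.** Section 3.5.2 says "During subsequent cycles chemistries are performed weekly" and names no day. The Appendix 2 calendar for cycles 3 and beyond supplies the days. General labs are marked on day 4 with a footnote, "h- CBC with differential only", on day 7 without a restriction, and once weekly after that. Two other tests already use blood on or around day 4:

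- the CBC, "twice weekly during administration prior to infusion, then weekly";
- coagulation studies, "Fibrinogen prior to day 1 and on days +4 and +8 of every cycle".

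Neither includes ALT or AST.

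**Earlier toxicity.** Section 1.3.4 describes the 12 patients treated before genotype selection: "Eight patients experienced transient, asymptomatic dose-limiting transaminitis" at 25 mcg/kg, and "This toxicity always occurred on day 4 of the infusion". The same section limits the source, since "systemic toxicities (cycle 1) were evaluated", and it gives no grades.

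**The hold rule.** For both grade 3 and grade 4 ALT/AST, section 3.3 says "Hold mithramycin therapy until recovery to Grade" 1 or lower. A grade 3 elevation that resolves within 21 days leaves the dose level unchanged. Grade 1 or 2 non-hematological events continue at full dose.

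**The concern.** A hold rule needs a laboratory value to act on. The trial's own data name day 4 as the day this toxicity appeared, and it was asymptomatic, so the twice-weekly toxicity assessment cannot be relied on to prompt a test. From cycle 3 the schedule omits ALT/AST on that day and next marks it on day 7, the last day of dosing. A patient whose value is already grade 3 or higher on day 4 keeps receiving drug that section 3.3 says should be held.

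The patients most exposed are those with a grade 3 elevation in cycle 2 that resolved within 21 days. Section 3.3 keeps their dose level, so they can start cycle 3 at 50 mcg/kg with one ALT/AST in the dosing week instead of seven. That is twice the dose at which the section 1.3.4 events were seen.

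What is at stake is patient safety in later cycles. Response rates, the two-stage rule and the other analyses are untouched, and the general easing of tests after cycle 2 is not questioned.

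**Working it through.** The plan states no figure on this point, so there is none to reproduce. The check is a count of doses.

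**Inputs**

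- Doses per cycle: 7, one a day on days 1 to 7 (section 3.2).
- ALT/AST in the dosing week from cycle 3: day 7 only (section 3.5.2 with Appendix 2, note h).
- Trigger for a hold: grade 3 or higher (section 3.3).
- Dose levels: 50, 30, 25 and 18 mcg/kg (section 3.3).
- Assumptions: ALT/AST is first grade 3 or higher on day 4, is still so on day 7, and dosing is not resumed within the week once held.

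**Doses given before the hold**

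A result read before the infusion on day *t* means *t* − 1 doses have been given. A result read after it means *t* doses.

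| Day 4 result read | Day 7 result read | Given with day 4 test | Given without | Difference |
|---|---|---|---|---|
| before infusion | before infusion | 3 | 6 | 3 |
| after infusion | after infusion | 4 | 7 | 3 |
| before infusion | after infusion | 3 | 7 | 4 |
| after infusion | before infusion | 4 | 6 | 2 |

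With equal turnaround the difference is 7 − 4 = 3 doses, or 3/7 = 43% of the cycle. If the day 4 result is read before that day's infusion, the difference is 3 or 4. For cycle 3 onward the documents do not say whether the day 7 chemistry is drawn before the infusion.

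**In dose terms (difference of 3)**

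| Dose level (mcg/kg) | 3 doses | Full cycle (7 doses) |
|---|---|---|
| 50 | 150 | 350 |
| 30 | 90 | 210 |
| 25 | 75 | 175 |
| 18 | 54 | 126 |

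If the day 4 value is grade 2 or lower, section 3.3 continues full dose and the difference is 0.

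**Averaged over later cycles**

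Let *p* be the chance of grade 3 or higher on day 4 of a later cycle. The average number of avoidable infusions per later cycle is 3 × *p*. The documents do not give *p*; the values below are assumptions.

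| Assumed *p* | 3 × *p* infusions | mcg/kg at the 50 level |
|---|---|---|
| 1% | 0.03 | 1.5 |
| 5% | 0.15 | 7.5 |
| 20% | 0.60 | 30 |

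The 8 of 12 (67%) in section 1.3.4 is not used as an estimate of *p*: it comes from cycle 1, in patients not selected by genotype, and without grades.

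**The case against.** The case for leaving the schedule alone is that it tapers monitoring by risk and that no document shows a later-cycle problem. The day 4 pattern comes from cycle 1 in a closed cohort enrolled without regard to genotype. Current patients have favorable genotypes and have had two cycles of daily chemistry, including the first 50 mcg/kg cycle if escalated. They drop to 25 mcg/kg after a dose-limiting toxicity in cycle 1. They receive dexamethasone through at least the first course, which is three cycles in section 3.2 and four in section 8.2. The earlier events were transient. Later cycles still have toxicity assessments twice weekly during dosing, day 7 and weekly ALT/AST, laboratory criteria before a further course (section 3.4), admission for out-of-town patients (section 3.1) and discretion to test or to stop treatment.

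Most of this stands as an argument about frequency. The later-cycle probability is unknown, probably lower than in section 1.3.4, and could be small enough to make the average effect negligible. It also stands that the count of three depends on equal turnaround. But none of these safeguards is a scheduled ALT/AST on day 4, and nothing prompts an unscheduled one in a patient without symptoms. Tolerance shown in cycles 1 and 2 was shown under dexamethasone, which is not assured after the first course.

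A further objection is that more holds in cycle 3 could affect evaluability, because section 8.2 ties it to receipt of a full course. That is a real but minor cost: the added holds would be ones that section 3.3 itself requires.

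**Conclusion.** The point holds. It is certain from the text that from cycle 3 no ALT/AST is scheduled on day 4 and that day 7 is the only one marked in the dosing week. Given a value of grade 3 or higher on day 4 that persists to day 7, the hold acts three of seven doses late with equal turnaround, and two to four otherwise.

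How often this would happen is not known, so confidence in its practical weight is medium. It is a recommended safety improvement, justified by the trial's own day 4 finding and a very low cost, and not a flaw in the design or the analysis.

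**What to change.** In section 3.5.2 and in the Appendix 2 calendar for cycles 3 and beyond, add ALT and AST to the day 4 pre-infusion draw, and require the result to be reviewed before dosing continues. Note h would then read CBC with differential plus ALT/AST. Leave the rest of the reduced schedule as it is.

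The cost is one extra assay per later cycle on blood already being drawn, a one-line change to section 3.5.2 and to note h, and possibly more dose holds, with the small effect on evaluability noted above.

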## **5 CORRELATIVE STUDIES / BIOSPECIMEN COLLECTION**

### **5.1 PHARMACOKINETIC (PK) SAMPLING**

Detailed plasma pharmacokinetic (PK) sampling of mithramycin will be performed prior to and at the completion of the first dose of mithramycin during cycle 1 and cycle 2 of course 1 (up to 11 tubes, Refer to details in [Appendix 3](#)). In addition, through and end of infusion samples will be obtained with the day 2, 4 and 7 doses to assess mithramycin accumulation, and samples will be obtained 24 and 48 hours after the day 7 dose of mithramycin on days 8 and 9, respectively. PK analysis will be performed at the NCI, Genitourinary Malignancies Branch (GMB). Samples will be stored in the TEL and batched and later transferred to the [name] Lab on dry ice for analysis. Please refer to section [5.3.2](#) for instructions on sample processing.

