13.3.3 Appendix 3: SAMPLE Pharmacokinetic and EKG Worksheet for Mithramycin CYCLE 1

TEL research sample # (2 10 mL red top tubes & 4 10 mL purple top tubes)	Coag reference sample # (obtain kit from TEL)	PK Sample # (two 3cc lavender top tube)	Hour (pre dose = within 1 hour prior to infusion)	Target Time	Actual Time	EKG Time	initials
C1D1	(date)						
R1	C1	PK 1	pre dose				
n/a	n/a	PK 2	3 h post-start of infusion			n/a	
n/a	n/a	PK 3	Just prior to the end of the 6 hour infusion			n/a	
n/a	n/a	PK 4	0.25 h post-infusion			n/a	
n/a	n/a	PK 5	0.5 h post-infusion			n/a	
n/a	n/a	PK 6	1 h post-infusion			n/a	
n/a	n/a	PK 7	2 h post-infusion			n/a	
n/a	n/a	PK 8	3 h post-infusion			n/a	
n/a	n/a	PK 9	5 h post-infusion			n/a	
n/a	n/a	PK 10	7 h post-infusion			n/a	
n/a	n/a	PK 11	9-12 h post-infusion			n/a	
C1D2	(date)						
n/a	n/a	PK 12	pre dose			n/a	
n/a	n/a	PK 13	end of infusion			n/a	
C1D4	(date)						
n/a	n/a	PK 14	pre dose			n/a	
n/a	n/a	PK 15	end of infusion			n/a	
C1D7	(date)						
n/a	n/a	PK 16	pre dose			n/a	
n/a	n/a	PK 17	end of infusion			n/a	
C1D8	(date)						
R2	n/a	PK 18	24 hrs p/dose #7			n/a	
n/a	n/a	PK 19	24.5 hrs/p dose #7			n/a	
C1D9	(date)						
n/a	n/a	PK 20	48 hrs/p dose #7			n/a	
n/a	n/a	PK 21	48.5 hrs/p dose #7			n/a	

13.3.4 Appendix 4: SAMPLE Pharmacokinetic and EKG Worksheet for Mithramycin CYCLE 2

TEL research samples (2 10 mL red top tubes & 4 10 mL purple top tubes)	Coag reference # (obtain kit from TEL)	PK Sample # (two 3cc lavender top tube)	Hour (pre dose = within 1 hour prior to infusion)	Target Time	Actual Time	EKG Time	initials
C2D1	(date)						
n/a	C 2	PK 1	pre dose				
n/a	n/a	PK 2	3 h post-start of infusion			n/a	
n/a	n/a	PK 3	Just prior to the end of the 6 hour infusion			n/a	
n/a	n/a	PK 4	0.25 h post-infusion			n/a	
n/a	n/a	PK 5	0.5 h post-infusion			n/a	
n/a	n/a	PK 6	1 h post-infusion			n/a	
n/a	n/a	PK 7	2 h post-infusion			n/a	
n/a	n/a	PK 8	3 h post-infusion			n/a	
n/a	n/a	PK 9	5 h post-infusion			n/a	
n/a	n/a	PK 10	7 h post-infusion			n/a	
n/a	n/a	PK 11	9-12 h post-infusion			n/a	
C2D2	(date)						
n/a	n/a	PK 12	pre dose			n/a	
n/a	n/a	PK 13	end of infusion			n/a	
C2D4	(date)						

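### The cycle 1-2 EKGs meant to evaluate QT prolongation are all pre-infusion, no scheduled EKG in any cycle falls near end-of-infusion concentration, and the cycle 1 worksheet omits two required EKGs

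*Combined protocol and SAP*

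**What the plan says.** All places are in the combined protocol and SAP.

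- **Section 3.5.2, cycles 1 and 2.** EKGs are set on "Days 1, 4, and 7, before infusion within 1 hour of pre infusion PK sample to evaluate for QT prolongation potential". This is the only purpose given for them. A note accepts EKGs outside the window, without a deviation, when unexpected events intervene.
- **Section 3.5.2, cycle 3 onward.** "Within 1 hour of start of infusion on day 1 and day 7", with no statement of whether this is before or after the start.
- **Appendix 2, study calendar.** Every on-treatment EKG cell, including cycle 3 onward, carries footnote "d -prior to dosing". The PK cells on days 1, 2, 4 and 7 also carry "f - end of infusion". No EKG cell does.
- **Section 5.1.** PK sampling already covers the end of infusion: "end of infusion samples will be obtained with the day 2, 4 and 7 doses". The worksheets add a day 1 sample, PK 3, timed "Just prior to the end of the 6 hour infusion".
- **Appendix 3, titled "SAMPLE Pharmacokinetic and EKG Worksheet for Mithramycin CYCLE 1".** The EKG cell is open only on the day 1 pre-dose row. It reads n/a on the day 4 and day 7 pre-dose rows (PK 14, PK 16). **Appendix 4**, for cycle 2, leaves those two cells open. Both worksheets show n/a on every row during, at the end of, or after an infusion.
- **Section 3.3.** Grade 3 or 4 QT prolongation leads to a cardiology consultation, with a dose consequence at grade 4 if therapy continues.

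**The concern.** An EKG schedule meant to assess QT potential should include a reading when drug concentration is high. This one places its readings where concentration is zero or at its lowest between doses. If QT change follows concentration, the scheduled readings would tend to understate it. A report of no QT prolongation could then be made only for drug-free and pre-dose exposure.

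The gap matters most from cycle 2, when patients who tolerated cycle 1 move to 50 mcg/kg (section 3.2). That is the highest exposure in the trial, and no EKG is scheduled at its peak. The QT row in section 3.3 also relies on an EKG that shows the effect.

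The worksheet mismatch is a separate matter. If staff followed the cycle 1 sheet, that cycle would yield only the drug-free day 1 EKG.

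**Working it through.** The plan gives no figure to reproduce here. The check is a side-by-side reading of the schedule, with an illustrative calculation.

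**Schedule**

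| EKG | Section 3.5.2 | Calendar | Worksheet |
|---|---|---|---|
| Cycle 1, day 1 | pre-infusion | pre-dose | open at pre-dose |
| Cycle 1, days 4 and 7 | pre-infusion | pre-dose | n/a |
| Cycle 2, days 1, 4 and 7 | pre-infusion | pre-dose | open at pre-dose |
| Cycle 3+, days 1 and 7 | within 1 h of start, side not stated | pre-dose | none |
| Any cycle, end of infusion | none | none | n/a in cycles 1-2 |

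**Inputs for the illustration**

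- 6-hour infusion once daily for 7 days, repeated every 21 days (+7/-3) (section 3.2). The gap from end of infusion to the next dose is 24 - 6 = 18 h.
- Human elimination half-life 10.6 h (±1.7), from three patients (section 1.3.2.1).
- Levels seen in this trial: "Peak and steady state mithramycin levels were 20 and 8nM, respectively" (section 1.3.4).
- Levels expected at 50 mcg/kg: Cmax about 40 nM and steady state about 20-25 nM (section 3.2).
- Assumption: one compartment. Section 1.3.2.1 calls elimination biphasic.

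**Day 1.** In cycle 1 no drug has been given. In cycle 2 the last infusion ended at hour 6 × 24 + 6 = 150 and the next cycle starts at hour 504, a gap of 354 h. With k = ln2/10.6 = 0.0654 per h, the residual is exp(-354k), about 9 × 10⁻¹¹ of the prior level. With an 18-day cycle the gap is 432 - 150 = 282 h and the residual is about 1 × 10⁻⁸. Both are effectively zero.

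**Days 4 and 7.** Pre-dose over end-of-infusion level on day n is exp(-18k) × acc(n-1)/acc(n), where acc(n) = (1 - exp(-24nk))/(1 - exp(-24k)).

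- exp(-18k) = 0.308.
- Taking the end of the first infusion as 1, day 4 is 0.386/1.261 = 0.306 and day 7 is 0.389/1.263 = 0.308. Both are about 31%.
- Over the ±1.7 h range, day 7 gives 25% at 8.9 h and 36% at 12.3 h.

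**From the protocol's own levels**, if steady state is read as trough:

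- observed: 8/20 = 40%;
- expected at 50 mcg/kg: 20/40 = 50% to 25/40 = 63%.

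**Cycle 3 onward, least favourable reading (1 h after the start).** On the same scale, one hour of infusion adds (1 - exp(-k))/(1 - exp(-6k)) = 0.195.

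- Day 1: 0.195/1, about 20% of that day's end-of-infusion level.
- Day 7: (0.389 × exp(-k) + 0.195)/1.263 = 0.443, about 44%.

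Under either reading, no scheduled EKG reaches the end-of-infusion level.

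**The case against.** **QT is not an endpoint.** It appears in none of the objectives in section 1.1, section 8 plans no QT analysis, and QT prolongation is not among the toxicities listed in sections 1.3.3 and 11.1.2 or Appendix 1. The EKGs act as safety monitoring, cycle 1 is inpatient, and nothing bars an unscheduled EKG. This limits the importance of the point. It does not remove it, because section 3.5.2 itself names QT evaluation as the purpose.

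**A pre-dose EKG has its own use.** In cycles 1-2 it is available before that day's dose and lines up with the daily pre-infusion chemistry, including potassium, ionized calcium and magnesium. Hypocalcemia and hypokalemia are listed drug effects (section 11.1.2, Appendix 1). This stands, and is the reason to keep the day 4 EKG where it is.

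**The worksheet is labelled a sample.** Section 3.5.2 and the calendar both require the EKGs, so the mismatch may be clerical. It is still a contradiction that needs correcting.

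**Stronger readings a reader might infer**

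- *Every EKG is before infusion and QT can never be seen at peak.* From cycle 3 the body text is ambiguous and only footnote d makes the EKG pre-dose. Off-window EKGs are tolerated, and a cardiology consultation could prompt more. What the documents support is that none is scheduled at peak.
- *Only 30-40% of the QT effect would be detected.* That omits the 50-63% implied by the protocol's own projection at 50 mcg/kg. It also assumes that steady state means trough and that QT effect is proportional to concentration without delay. The documents say neither.
- *The ratio could be as low as 8%.* That uses the 5 h monkey half-life although a human value is given.

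**Conclusion.** The point holds, and the schedule should be changed. In cycles 1-2 the EKGs set to evaluate QT potential are all pre-infusion, and no scheduled EKG in any cycle falls at or near end-of-infusion concentration, including at 50 mcg/kg. The conclusion rests on the schedule alone, on which section 3.5.2, the calendar and the worksheets agree.

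The size, roughly 30-63% of peak concentration on days 4 and 7 and effectively zero on day 1, is illustrative. Its lower end depends on a half-life from three patients and a one-compartment form. Its upper end depends on reading steady state as trough. It does not measure any QT effect, and a delayed effect is not addressed in the documents.

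Two inconsistencies stand on their own and must be reconciled: the cycle 3+ body text against footnote d, and the cycle 1 worksheet against section 3.5.2, the calendar and the cycle 2 worksheet. The primary response endpoint is unaffected.

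**What to change.** - Keep the day 1 pre-dose EKG as baseline, and keep the day 4 pre-dose EKG in cycles 1-2.
- Retime the existing day 7 EKG to the last hour of the 6-hour infusion in every cycle. In cycles 1-2, pair it with PK 17, which is already drawn.
- Report QTc change from day 1 pre-dose, with the paired concentration where PK is taken.
- In section 3.5.2, state for cycle 3 onward that the day 1 EKG is before infusion, and give the new day 7 timing. Give the day 7 EKG cells in the calendar a matching footnote.
- In Appendix 3, remove the n/a on the day 4 pre-dose row (PK 14). In Appendices 3 and 4, open the EKG cell on the day 7 end-of-infusion row (PK 17) and close it on the day 7 pre-dose row (PK 16). If day 7 is not retimed, the n/a on PK 16 in Appendix 3 must be removed as well.

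**Cost.** Wording, one calendar footnote and a few worksheet cells, with no added EKG or blood draw. The day 7 pre-dose EKG is lost. Cycles 1-2 keep an on-drug pre-dose EKG on day 4, but from cycle 3 none remains. A patient whose dosing stops before day 7 gives no end-of-infusion EKG in that cycle. The QT action rule in section 3.3 is not touched.
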